6.4 Long Term Follow Up (12 months to 5 years)

After the 6 month visit, subjects must be evaluated at the Clinical Center at 12 months (+/- 30 days) and then yearly thereafter to 5 years (+/- 90 days for Years 1 & 2; +/- 1 Year for Years 3 & 4). Subjects will be seen by their home physician as clinically indicated and the Hematology Branch investigators and home physicians will remain in communication. Home physicians will monitor blood counts and other clinical parameters as clinically indicated. The following tests will be performed at each Clinical Center visit. At the clinical investigator's discretion, participants may be evaluated more frequently if medically indicated based on disease status. If a subject is unable to present to CC for landmark Year 3 or 4 follow up due to circumstances beyond their control and their peripheral blood counts are available and stable compared to last visit at CC, the subject may remain on the study and follow up as soon as able but no longer than 1 year from the missed visit.

- Complete blood counts with differential
- Acute care, Mineral, Hepatic and Other panel
- Reticulocyte count
- Bone marrow aspiration and core biopsy, to be stained for standard morphologic analysis and quantitation of cellularity with hematoxylin and eosin, and special stains to assess reticulin and collagen, primitive stem and progenitor cells via CD34 immunohistochemistry, and other lineage-specific or special stains as indicated to classify any abnormalities.
- Bone marrow chromosomal analysis via standard cytogenetic techniques
- Flow cytometry of the peripheral blood to quantitate GPI-negative cells
- Lymphocyte peripheral blood phenotyping
- HRQL survey administration (Surveys will not be required for the Extension and Exploratory Laboratory Cohorts.)

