7. CRITERIA FOR RESPONSE

Response is defined as blood counts no longer meeting the standard ("Camitta") criteria for severe pancytopenia in SAA (see section 4.1), equivalent to 2 of the following values obtained on 2 serial blood count measurements at least one week apart at landmark time points (3, and 6 months)

- Absolute neutrophil count $\geq 500/\mu\text{L}$
- Platelet count $\geq 20,000/\mu\text{L}$
- Reticulocyte count $\geq 60,000/\mu\text{L}$

A complete response (CR) will be defined as (all 3 must be met):

- Absolute neutrophil count $\geq 1,000/\mu\text{L}$
- Platelet count $\geq 100,000/\mu\text{L}$
- Hgb $\geq 10 \text{ g/dL}$

A partial response will be defined as blood counts that do not meet criteria for severe pancytopenia but are not sufficient for a CR.

Improvement in counts that are dependent upon exogenously administered growth factors or transfusion will not be considered as fulfilling response criteria.

The presence of evolution to PNH will be defined by flow cytometric detection of $> 1\%$ GPI-deficient

neutrophils at baseline and landmark time points through 5 years. Evolution to myelodysplasia and/or acute leukemia will be assessed at landmark time points, or as clinically indicated between landmarks by examination of peripheral blood and bone marrow and diagnosis and classification according to the WHO criteria. Evolution to clonal hematopoiesis will be defined by detection of new bone marrow cytogenetic abnormalities at landmark time points.

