9.4 Secondary Endpoints

Secondary endpoints will also be evaluated for the study to include: (a) hematological response at 3 and 12 months and yearly thereafter; (b) relapse (c) clonal evolution to PNH, clonal chromosomal population in bone marrow, myelodysplasia by morphology, or acute leukemia; (d) survival; (e) health-related quality of life; (f) hematological response of relapse subjects that re-start treatment; and (g) affects of a 2.0mg/kg/day CsA dose starting month 6 for 18 months until month 24 on the rate of relapse of subjects deemed responders at month 6.

Subjects will be followed up to 60 months so that long-term disease-free and overall survival can be estimated. Response and toxicity comparisons will also be made with the results obtained from prior NHLBI studies: the h-ATG/CsA protocol (90-H-0146); the h-ATG/CsA vs. Cytoxan/CsA protocol (97-H-0117); the h-ATG/CsA/MMF protocol (00-H-0032); the h-ATG/CsA/Rapamune protocol (03-H-0193); the 3-arm randomized study (06-H-0034) and the r-ATG vs. alemtuzumab (03-H-0249) trials.

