Completion of protocol participation: After 5 years, protocol participation will be deemed complete. Once off study, subjects will be referred back to the referring physician or consented to the Hematology Branch evaluation and treatment protocol (94-H-0010) or evaluated for eligibility for another Branch protocol, depending on the wishes of the subject and availability of appropriate additional clinical trials at the NIH.

Death: Death of Subject

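### Section 7 counts a new cytogenetic abnormality only at landmark visits, so a clone found between them can go uncounted; separately, the overlapping windows in section 6.4 leave late yearly response without an unambiguous year.

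*Combined protocol and SAP*

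**What the plan says.** Section 7 treats two forms of evolution differently in adjacent sentences. MDS and leukemia are assessed at landmarks "or as clinically indicated between landmarks by examination of peripheral blood and bone marrow". For the cytogenetic component the text is: "Evolution to clonal hematopoiesis will be defined by detection of new bone marrow cytogenetic abnormalities at landmark time points". It has no between-landmark clause.

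Unscheduled marrows are foreseen. Section 6.4 allows extra evaluations when medically indicated, and section 6.5 lists marrow and cytogenetics among the tests that may be done when drug is restarted for relapse.

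Section 6.4 sets the annual visits and their windows with the words "then yearly thereafter to 5 years (+/- 90 days for Years 1 & 2; +/- 1 Year for Years 3 & 4". The same sentence gives the first of the long-term visits its own, narrower window: "subjects must be evaluated at the Clinical Center at 12 months (+/- 30 days". A subject who misses the Year 3 or 4 visit for reasons outside their control has an allowance: "the subject may remain on the study and follow up as soon as able but no longer than 1 year from the missed visit". One condition attached to this allowance is that "their peripheral blood counts are available and stable compared to last visit at CC". Section 9.6 adds: "After 5 years, protocol participation will be deemed complete".

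Among the secondary endpoints in section 9.4 are "hematological response at 3 and 12 months and yearly thereafter" and clonal evolution, where a chromosomal clone in the marrow is listed apart from morphologic myelodysplasia. Section 9.2 compares clonal evolution with historical rates of 15-20% (any clone) and 10-15% (high risk).

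**The concern.** The section 7 wording leaves out clones found because a subject was unwell enough to need an extra marrow. Such a subject may die, be transplanted or leave the study before the next landmark, so the abnormality may never be seen again at a qualifying visit. Any miscount runs one way, towards a lower rate for the new regimen.

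This endpoint carries weight in the plan. Section 9.1 uses CR as a surrogate for late events. Section 2.9.1 gives a possible reduction in cytogenetic evolution as a reason for shortening eltrombopag in cohort 2. Section 2.6 reports new cytogenetic abnormalities in 8 of 43 earlier patients. Section 9.5 keeps clonal evolution out of the stopping rules, so the endpoint count is where a signal would appear.

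The windows raise a separate question. A window of one year either side of an annual visit lets one visit serve two landmarks, and sections 6.4, 7, 9.2 and 9.4 do not say which year that visit belongs to.

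**Working it through.** The plan states no figure that depends on this point, so there is none to reproduce.

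**1. The two definitions side by side (section 7)**

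| Event | Found at a landmark | Found between landmarks |
|---|---|---|
| MDS/AML | counted | counted |
| New cytogenetic abnormality, not MDS/AML | counted | outside the definition |

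A clone is lost only if it is found off-landmark, does not meet MDS/AML, and is not seen at a later landmark.

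**2. Windows in months (section 6.4; 90 days taken as 3 months).** The year labels can be read as study years, or as years counted after the 12-month visit.

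| Landmark | Study years | Years after month 12 |
|---|---|---|
| 12 | 11-13, or 9-15 as Year 1 | 11-13 |
| 24 | 21-27 | 21-27 |
| 36 | 24-48 | 33-39 |
| 48 | 36-60 | 36-60 |
| 60 | none given | 48-72 |

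Overlap = smaller upper limit minus larger lower limit:
- Study years: months 24 and 36 overlap by 27 - 24 = 3 months; months 36 and 48 by 48 - 36 = 12 months.
- Years after month 12: months 36 and 48 overlap by 39 - 36 = 3 months; months 48 and 60 by 60 - 48 = 12 months. The last window runs 72 - 60 = 12 months past the completion point in section 9.6.
- Months 12 (+/- 30 days) and 24 do not overlap: (730.5 - 90) - (365.25 + 30) = 245 days apart.

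**3. Where an off-landmark marrow can fall,** if a marrow inside a window is taken as that landmark's marrow:
- Before month 21 (day 640), the windows cover 20 days at month 3, 20 at month 6 (both +/- 10 days, section 6.3) and 60 at month 12. That is 100 days covered and 640 - 100 = 540 uncovered. With +/- 90 days at month 12 it is 220 covered and 420 uncovered.
- After month 21, study years: 21-27, 24-48 and 36-60 run together, so nothing is uncovered to month 60.
- After month 21, years after month 12: only months 27-33 are uncovered (days 820 to 1006, or 186 days).

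**4. Longest permitted spacing** between consecutive landmark marrows is 60 - 24 = 36 months (study years) or 72 - 36 = 36 months (the other reading).

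**5. Size per clone.** One uncounted clone in a cohort of 31 lowers the rate by 1/31 = 3.2 points. The 15-20% benchmark corresponds to 31 x 0.15 = 4.65 to 31 x 0.20 = 6.2 subjects. This is arithmetic per subject, not a forecast.

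**The case against.** Several stronger conclusions are tempting, and the documents do not support them.

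- **That clones cannot be placed in a year.** Section 9.4 gives clonal evolution no yearly breakdown, and section 9.2 compares an overall rate. The sample date places the detection; only true onset is uncertain between marrows. Of these two endpoints, only response is yearly.
- **That the two defects compound.** They largely offset each other. If any marrow inside a window counts as a landmark marrow, the wide late windows capture nearly everything after month 21.
- **That marrows will be three years apart.** That needs one visit a full year early and the next a full year late. Section 6.4 keeps visits yearly and treats a late visit as an exception, and section 6.5 requires relapsed subjects who restart drug to be seen at least annually.
- **That the historical comparison is shown to be biased.** How clones were counted in the earlier protocols is not given. The 10-15% high-risk benchmark also includes high-risk MDS and leukemia, and MDS/AML found between landmarks is counted here. The any-clone 15-20% is the closer comparator.
- **That yearly response is unmeasurable.** Response rests on blood counts, and section 9.7 has home laboratory values entered in the database. However, section 7 names response landmarks only at 3 and 6 months, so how later years are to be scored remains unstated.

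It can also be said that section 7 may be incomplete drafting, since sections 9.4 and 9.5 speak of clonal evolution without a landmark limit, and that accrual was nearly complete (178 of 182, section 2.9.4). Both are fair. They argue for aligning the text and recording when it was changed, not for leaving a definition that says less than intended.

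**Conclusion.** The concern holds in a limited form. The section 7 definition, read literally, omits a new cytogenetic clone found off-landmark that is not MDS/AML and is not seen again. Mainly this exposes the roughly 420 to 540 days before month 21 that no landmark window covers, assuming that any marrow inside a window counts for that landmark. The effect would be to understate clonal evolution by 3.2 points per missed clone in a cohort of 31. The number missed cannot be derived from the documents.

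The windows in section 6.4 overlap under either reading. On the study-year reading, month 12 has two windows and Year 5 has none. With no assignment rule, yearly response at the visits with one-year windows and their neighbours cannot be assigned unambiguously. The allowance for a late visit also does not fit a window that already permits the same delay without conditions. Because that allowance depends on stable counts, it ties the timing of a marrow to the subject's course.

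Months 3, 6, 12 and 24 are separable from one another. The primary endpoint, CR at 6 months, is unaffected. This is worth correcting but does not threaten the main result.

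**What to change.** 1. In section 7, define cytogenetic evolution as a new abnormality in any marrow sample after baseline, at or between landmarks, dated by the sample. This matches the MDS/AML sentence beside it.
2. In section 6.4, state which month each window applies to. Reconcile the two month-12 windows, the Year 5 window and the late-visit allowance.
3. For analysis, assign each visit to the single nearest annual landmark with non-overlapping analysis windows. The midpoints between annual landmarks are months 18, 30, 42 and 54; add a rule for ties and for two visits in one window. Analyse clonal evolution by actual sample date.
4. Because outcome data already exist, record the date of the change and report the clonal evolution count under both the literal and the corrected definition.

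The cost is protocol wording and some re-derivation of existing data. No visit or procedure is added, and scheduling for staying on study need not change. The downside is that some late visits will leave a landmark missing, and the clonal evolution rate may be slightly less favourable.

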6.5 Extended Access for Relapse

Indicated below are the procedures that can be performed on subjects that re-start drug due to relapse. At the clinical investigator's discretion, participants may be evaluated as medically indicated based on disease status. The procedures may be performed by the subjects' home physician or at the Clinical Center. If testing is done by home physician, progress notes and laboratory results from home physician will be sent to the research team. Subjects will be seen at the Clinical Center as clinically indicated while on extended access for relapse, but no less than annually until 5 years. Below is the list of procedures that will be performed as medically indicated.

Procedures that may be performed when drugs are re-started

- History and physical examination
- Pregnancy test (urine or blood HCG in women of child bearing potential)
- Complete blood counts with differential
- Chemistry panel (NIH Acute care, Mineral, Hepatic and Other panel, home laboratory chemistry panel must include electrolytes, hepatic transaminases, urea nitrogen (BUN), serum creatinine, total bilirubin, and reticulocyte count)
- CsA blood level will be monitored until levels are stabilized in the therapeutic range of 200 – 400 ng/ml. CsA dosage will be adjusted to target this range. More frequent drug serum levels may be obtained as needed to achieve target therapeutic levels and avoid toxicity.
 - Bone marrow aspiration and core biopsy, to be stained for standard morphologic analysis and quantitation of cellularity with hematoxylin and eosin, and special stains to assess reticulin and collagen, primitive stem and progenitor cells via CD34 immunohistochemistry, and other lineage-specific or special stains as indicated to classify any abnormalities.
 - Bone marrow chromosomal analysis via standard cytogenetic techniques Flow cytometry of the peripheral blood to quantitate GPI-negative cells
 - Lymphocyte peripheral blood phenotyping

7. CRITERIA FOR RESPONSE

Response is defined as blood counts no longer meeting the standard ("Camitta") criteria for severe pancytopenia in SAA (see section 4.1), equivalent to 2 of the following values obtained on 2 serial blood count measurements at least one week apart at landmark time points (3, and 6 months)

- Absolute neutrophil count $\geq 500/\mu\text{L}$
- Platelet count $\geq 20,000/\mu\text{L}$
- Reticulocyte count $\geq 60,000/\mu\text{L}$

A complete response (CR) will be defined as (all 3 must be met):

- Absolute neutrophil count $\geq 1,000/\mu\text{L}$
- Platelet count $\geq 100,000/\mu\text{L}$
- Hgb $\geq 10 \text{ g/dL}$

A partial response will be defined as blood counts that do not meet criteria for severe pancytopenia but are not sufficient for a CR.

Improvement in counts that are dependent upon exogenously administered growth factors or transfusion will not be considered as fulfilling response criteria.

The presence of evolution to PNH will be defined by flow cytometric detection of $> 1\%$ GPI-deficient

neutrophils at baseline and landmark time points through 5 years. Evolution to myelodysplasia and/or acute leukemia will be assessed at landmark time points, or as clinically indicated between landmarks by examination of peripheral blood and bone marrow and diagnosis and classification according to the WHO criteria. Evolution to clonal hematopoiesis will be defined by detection of new bone marrow cytogenetic abnormalities at landmark time points.

Relapse: Clinical definition determined by observation of a decline in blood counts not explained by another clinical process (e.g. acute infection) that is either (a) a substantial decline in one or more blood counts, or (b) a progressive decline in one or more blood counts on at least two consecutive blood draws. The date of relapse will be recorded into the clinical database as the date the participant resumed immunosuppression with CsA or required higher doses of CsA if on the low dose prior to the 2-year landmark visit. A description of how the clinical assessment was made by the PI will be recorded in the clinical database. To corroborate the relapse, the most recent blood counts collected prior to the date of relapse will be recorded into the clinical database with the following parameters: absolute neutrophil count, or neutrophil percentage and white blood cell count if ANC is not available, hemoglobin, absolute reticulocyte count (or reticulocyte percentage and RBC if absolute reticulocyte count is not available) and platelets.

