4.2 Exclusion Criteria

- 4.2.1 Known diagnosis of Fanconi anemia
- 4.2.2 Evidence of a clonal disorder on cytogenetics performed within 12 weeks of study entry.
Patients with super severe neutropenia (ANC < 200 / μ L) will not be excluded initially if cytogenetics are not available or pending. If evidence of a clonal disorder consistent with myelodysplasia is later identified, the patient will go off study – see section 9.6
- 4.2.3 Prior immunosuppressive therapy with any ATG, alemtuzumab, or high dose cyclophosphamide
- 4.2.4 SGOT or SGPT > 5 times the upper limit of normal
- 4.2.5 Subjects with known liver cirrhosis in severity that would preclude tolerability of cyclosporine and eltrombopag as evidenced by albumin < 35g/L
- 4.2.6 Hypersensitivity to eltrombopag or its components
- 4.2.7 Infection not adequately responding to appropriate therapy

- 4.2.8 Moribund status or concurrent hepatic, renal, cardiac, neurologic, pulmonary, infectious, or metabolic disease of such severity that it would preclude the patient's ability to tolerate protocol therapy, or that death within 7-10 days is likely
- 4.2.9 Potential subjects with cancer who are on active chemotherapeutic treatment or who take drugs with hematological effects will not be eligible
- 4.2.10 Current pregnancy, or unwillingness to take oral contraceptives or use a barrier method of birth control or practice abstinence to refrain from pregnancy if of childbearing potential during the course of this study
- 4.2.11 Inability to understand the investigational nature of the study or to give informed consent or does not have a legally authorized representative or surrogate that can provide informed consent per section 11.6.

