6. CLINICAL MONITORING

Samples will be ordered and tracked through the CRIS Screens. Should a CRIS screen not be available, the NIH form 2803-1 will be completed and will accompany the specimen and be filed in the medical record. HRQL surveys will be mailed to the subject if they are not required to return to the NIH CC for study evaluations.

6.1 Pre-study Evaluation - PI may accept results from studies done outside of NIH.

Baseline studies will be conducted as follows:

- Medical history and physical examination
- Concurrent medication review
- HRQL survey administration (Surveys will not be required for the Extension and Exploratory Laboratory Cohort)
- Baseline clinical studies
 - Complete blood count with differential
 - Reticulocyte count
 - DAT (direct antiglobulin test)
 - Type and screen
 - Acute Care (Na, K, Cl, CO₂, Creatinine, Glucose, and Urea Nitrogen), Mineral (Phosphorus, Magnesium, Albumin, and Calcium), Hepatic (Alk Phosphatase, ALT, AST, Total Bilirubin, and Direct Bilirubin), and Other (Total Protein, CK, Uric Acid, and LD panel)
 - Coagulation and thrombosis screens (PT, PTT, D-dimer)
 - Thyroid function tests
 - Viral serologies for hepatitis A, B, C, HIV, HSV, EBV and CMV
 - EBV and CMV PCR
 - PPD (at risk subjects only, based on history or geography)
 - Folate level
 - B12 level
 - Iron panel (ferritin, transferrin, % saturation)
 - HLA typing (if not already available)
 - Pregnancy test (urine or blood HCG in women of child bearing potential)
 - Bone marrow aspiration and core biopsy, to be stained for standard morphologic analysis and quantitation of cellularity with hematoxylin and eosin, and special stains to assess reticulin and collagen, primitive stem and progenitor cells via CD34 immunohistochemistry, and other lineage-specific or special stains as indicated to classify any abnormalities.
 - Bone marrow chromosomal analysis via standard cytogenetic techniques
 - Telomere length of leukocytes
 - Flow cytometry of the peripheral blood to quantitate GPI-negative cells
 - Lymphocyte peripheral blood phenotyping (analysis of T, B, and NK subsets via flow cytometry)
 - Chest X-ray- this does not need to be performed if a clinically indicated chest CT is performed to reduce the radiation burden

- EKG
- Placement of a central line if subject does not have a pre-existing indwelling central venous catheter

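### Section 7 does not require evolution to PNH to be new since baseline, so a clone present at entry counts as an event; a lesser gap leaves some relapses undated

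*Combined protocol and SAP*

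**What the plan says.** **PNH.** Section 9.4 lists as secondary endpoint (c) "clonal evolution to PNH, clonal chromosomal population in bone marrow, myelodysplasia by morphology, or acute leukemia". Section 7 supplies the working definition: "The presence of evolution to PNH will be defined by flow cytometric detection of" more than 1% GPI-deficient "neutrophils at baseline and landmark time points through 5 years". Later in the same paragraph the cytogenetic outcome is defined differently: "Evolution to clonal hematopoiesis will be defined by detection of new bone marrow cytogenetic abnormalities", assessed at the landmark visits.

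The related exclusion (4.2.2) is "Evidence of a clonal disorder on cytogenetics performed within 12 weeks of study entry". No criterion in Section 4.2 refers to GPI-negative cells. The test "Flow cytometry of the peripheral blood to quantitate GPI-negative cells" is scheduled before treatment (6.1), at months 3 and 6 (6.3), and at month 12 and yearly after that (6.4).

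**Relapse.** Section 7 defines the event as a fall in blood counts with no other clinical explanation. The fall must be either substantial or progressive over at least two consecutive draws. The date rule is narrower: "The date of relapse will be recorded into the clinical database as the date the participant resumed immunosuppression with CsA or required higher doses". The second limb, a cyclosporine increase, applies to subjects on the low dose before the two-year visit. The supporting counts depend on that date: "To corroborate the relapse, the most recent blood counts collected prior to the date of relapse will be recorded into the clinical database". Section 5.7 lets relapse in cohorts 1 and 2 be managed with eltrombopag, cyclosporine or both. In cohort 3 and the extension cohort, an eltrombopag restart and a cyclosporine increase are each optional.

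**The concern.** An evolution endpoint should measure something that arises after treatment starts. The PNH sentence sets a threshold and a list of time points, but it does not compare the later value with the first. Two analysts with identical data could report different rates for endpoint (c): one would count every subject above 1%, the other only those who crossed 1% on study. The cohorts are not randomized and have no concurrent control, so nothing in the results would show that an entry clone had been reported as a post-treatment outcome.

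The relapse gap is smaller. A relapse managed without a cyclosporine change is still a relapse, but Section 7 gives it no date and so does not identify which blood counts should corroborate it. This bears on any analysis that places relapses in time. For endpoint (g), the month 6 to 24 relapse rate on low-dose cyclosporine, it matters mainly for relapses near the ends of that window.

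**Working it through.** The plan states no figure on this point that could be reproduced. The check is a comparison of text, followed by per-case arithmetic.

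**Step 1. Can a clone be present at entry?** Yes. Exclusion 4.2.2 works through cytogenetics, and the other criteria in Section 4.2 do not mention GPI-negative cells. The pre-study flow result in Section 6.1 is recorded but does not affect eligibility.

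**Step 2. Does such a clone meet the definition?** There are three possible readings of the Section 7 sentence.
- If baseline is a detection time point, a baseline value above 1% meets the rule by itself.
- If baseline is only the reference measurement, a clone above 1% at entry and still above 1% at a landmark meets the rule, because no comparison with the reference is stated.
- If the word evolution is taken to imply newness, the clone does not count. This reading needs a condition that the sentence lacks and that the cytogenetic sentence in the same paragraph contains.

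**Step 3. Does another section supply the condition?** No. Sections 9.2 and 9.4 give neither an at-risk denominator nor a change-from-baseline rule for PNH.

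**Step 4. Size per case.** Inputs are 31 subjects per cohort (cohort 2 also enrolled 31) and 87 in the extension cohort (title page, Section 9.1).
- Cohort of 31: 1/31 = 3.2 points per entry clone counted.
- Extension cohort: 1/87 = 1.1 points per entry clone counted.

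Let k be the number of subjects with an entry clone and m the number with a truly new one. The rule as written gives (k + m)/n; a rule restricted to subjects at risk gives m/(n − k). The documents give neither k nor m, so the values below are assumptions that only show how the two rules diverge, with m = 1 and n = 31:

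| k (assumed) | Rule as written | At-risk rule |
|---|---|---|
| 0 | 1/31 = 3.2% | 1/31 = 3.2% |
| 1 | 2/31 = 6.5% | 1/30 = 3.3% |
| 3 | 4/31 = 12.9% | 1/28 = 3.6% |

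**Step 5. Relapse date.** Set Section 5.7 beside Section 7. A subject who relapses and restarts eltrombopag alone has neither resumed cyclosporine nor needed a higher dose, so neither limb of the date rule applies. The same holds for a cohort 2 subject who relapses between months 3 and 6 on full-dose cyclosporine and restarts only eltrombopag. Section 5.7 makes that subject a non-responder at month 6 but gives no relapse date. The event definition does not depend on treatment, so in each case the event stands and only its date is missing.

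**The case against.** The strongest defence on PNH is that a subject cannot evolve at baseline. On this view the sentence only fixes an assay threshold and a measurement schedule, and baseline is the reference. That may well be the intent, and since flow is done at every relevant visit, new and pre-existing clones can be separated. No section says that entry clones will be counted. What remains is that the operative definition does not say they will not be, while its neighbour in the same paragraph does.

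On relapse, Section 5.2 reports that early relapses after month 6 were salvaged by resuming cyclosporine, so the date rule may fit many cases. The investigator's description of the assessment is also recorded, so a date can probably be recovered. Both points stand and make this part minor.

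A reader might infer more than the documents support:
- **Relapses managed without cyclosporine drop out of the relapse rate.** Section 7 defines relapse by blood counts whatever the treatment, and no section says undated relapses are omitted.
- **A planned time-to-relapse analysis is compromised.** Section 9.2 names cumulative incidence of response, time to complete response and survival analysis, but not time to relapse.
- **Pregnancy (11.3) and mycophenolate (9.6) leave many more relapses undated.** Section 11.3 rules out only on-protocol retreatment. Section 9.6 concerns patients who cannot tolerate cyclosporine, and its use for relapse would be an inference. Both add little to endpoint (g).
- **The historical comparison is biased by a known amount.** The 15-20% rate in Section 9.2 is for any clonal abnormality and is not stated to include PNH.

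**Conclusion.** The PNH definition is wrong as written and should be corrected. Applied literally, it counts clones present at entry as evolution after treatment, at 3.2 points per subject in a cohort of 31 and 1.1 points in the extension cohort. These figures assume that every enrolled subject is in the denominator. No total can be given, because the documents do not report how many subjects had more than 1% GPI-deficient neutrophils at baseline; if none did, the effect is zero.

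The relapse point is minor. Relapses managed with eltrombopag alone count as events but have no stated date and no anchor for the corroborating counts. Their number is not given.

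Both points concern secondary endpoints only. The primary endpoint, complete response at six months, and the stopping rules do not use either definition.

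**What to change.** **PNH.** In Section 7, define evolution to PNH as more than 1% GPI-deficient neutrophils at a post-baseline landmark in a subject with 1% or less at baseline. Use subjects at 1% or less at baseline as the denominator. Report baseline clones and their change over time separately. This costs only wording and a derived variable, because baseline and landmark flow are already collected.

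**Relapse date.** Keep the cyclosporine-change date. Where no cyclosporine change occurs, record a stated fallback, such as the date of the investigator's clinical determination of relapse or of the first relapse treatment of any kind, and tie the corroborating counts to it. The first qualifying blood draw would be a weaker choice: a substantial decline has no numerical threshold, and home counts after month 6 are taken as clinically indicated (6.4). Sections 5.7 and 7 need to be reconciled on the date only; no view is taken on how relapse should be treated. The cost is one date field and a look back through the records of past relapses that had no cyclosporine change. Neither change needs a new patient procedure.
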